#### **8.7.3. Imputation of missing data on baseline characteristics in Flatiron RWD**

Previous analyses of the Flatiron data have found that there are moderate to large amounts of missing data on baseline characteristics such as ECOG performance score and LDH. As analyses restricted to patients with non-missing data are highly likely to be biased, imputation of missing data on key baseline characteristics is needed to ensure that adjusted analyses of OS between the trial and RWD settings are based on all eligible patients.

In this study, multivariate imputation by chained equations (MICE) will be used to impute missing data on baseline characteristics. Briefly, the MICE method imputes data for a missing patient characteristic based on iterative regressions of observed data for that characteristic on observed and imputed values of other baseline characteristics. This process will be repeated for each characteristic until stable estimates are obtained, and the entire procedure will be repeated so that multiple datasets with imputed values for baseline characteristics are created.

Baseline characteristics to be imputed will include ECOG performance score, LDH and disease stage. Additional variables will be considered for inclusion in the MICE procedure based on their relevance for adjustment and degree of missingness in the study sample. As recommended in the literature, the MICE approach will be used to create multiple datasets (e.g., 100 datasets) with imputed values, which will be used and combined in subsequent analyses.

Analyses of baseline characteristics in RWD described in [Section 8.7.1](#) will be repeated for each imputed dataset, and then summarized across all imputed datasets.

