There is increasing interest in using real-world data (RWD) to evaluate effectiveness of encorafenib plus binimatinib (ENCO+BINI). One important use of the emerging RWD for ENCO+BINI is to assess how clinical effectiveness in real-world practice compares to efficacy observed in clinical trials. Clinical trial data (CTD) and real-world data on ENCO+BINI may also be pooled to provide a larger sample size for future evidence generation studies, provided outcomes are sufficiently consistent between CTD and RWD settings.

However, use of RWD presents important challenges. In general, differences in baseline characteristics between patients enrolled in clinical trials and patients receiving treatment in RWD settings can result in bias. While this concern can be mitigated with adequate statistical adjustment, missing data in RWD sources on key confounders of outcomes may also hamper ability to adjust for such baseline differences. Suitability of RWD for specific uses therefore needs to be assessed on a case-by-case basis considering details of the RWD data source and outcomes of interest.

In this study, we will compare overall survival (OS) between patients receiving ENCO+BINI in the Phase 3 COLUMBUS trial versus in the Flatiron Health Electronic Health Records (EHR) database. Baseline profiles of patients will also be compared across these settings to characterize differences in patients receiving ENCO+BINI and adjustments will be made for differences in baseline factors associated with OS. Missingness for key baseline characteristics will be addressed using a multiple imputation approach that has been validated for Flatiron Health EHR data in metastatic melanoma. This study will help contextualize real-world clinical effectiveness of ENCO+BINI, and assess the

suitability of pooling CTD and RWD on ENCO+BINI from these 2 sources for use in future RWE studies.

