#### **8.7.4. Adjusted analysis of OS between ENCO+BINI cohorts in Columbus trial versus in Flatiron RWD**

Finally, an adjusted comparison of OS between ENCO+BINI cohorts in the Columbus trial and Flatiron RWD will be conducted. Hazard ratios will be estimated based on a multivariable Cox proportional hazard model, adjusting for key baseline characteristics known or expected to be related to OS in metastatic melanoma (e.g., age, sex, race, body mass index, ECOG performance score, disease stage, LDH, time from diagnosis to metastatic disease, time from metastatic diagnosis to ENCO+BINI initiation and use of prior therapies). Specific adjustment factors listed here may be revised based on expert clinical input.

The adjusted analyses will be conducted using the Columbus trial dataset and each of the RWD datasets with imputed baseline characteristic values in turn. Log-hazard ratios for the difference in OS with ENCO+BINI between the Columbus trial and each imputed dataset will be obtained, and a summary HR obtained by pooling results across all imputed datasets will be generated using Rubin's rules.

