### 8.7.5. Exploratory analyses of PFS

Analyses assessing PFS will also be explored. PFS will be summarized for ENCO+BINI cohorts in the Columbus trial and in Flatiron RWD. In CTD, PFS will be defined as the time from the date of randomization to the date of the first documented disease progression or death due to any cause, whichever occurred first; if a patient did not have an event at the analysis cutoff date, PFS will be censored at the date of the last adequate tumor assessment. In RWD, PFS will be defined as the time from the index date to either the date of first disease progression event or death in the absence of progression; patients without disease progression or death will be censored at the last date the patient could have been assessed for progression (e.g., the last clinical note date) or the end of the follow-up period, whichever occurs first.

Suitability of comparative analyses of PFS between ENCO+BINI cohorts in the Columbus versus in Flatiron RWD will be determined following additional data exploration to characterize number and frequency of assessments of PFS available in these settings, and discussion of comparability of the assessment of disease progression in RWD vs CTD. If analyses of PFS are deemed suitable based on these evaluations, unadjusted and adjusted comparisons of PFS will be conducted using the methods described in Sections 8.7.2 and 8.7.4.

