### ANNEX 1. LIST OF STAND-ALONE DOCUMENTS

None.

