Treatment-Related Characteristics		
Prior therapies, n (%)		
Treatment naive	XX (XX.X)	XX (XX.X)
Disease progression after 1L IO	XX (XX.X)	XX (XX.X)
Prior systemic therapies, n (%)		
Any therapy	XX (XX.X)	XX (XX.X)
Medication	XX (XX.X)	XX (XX.X)
Surgery	XX (XX.X)	XX (XX.X)
Radiotherapy	XX (XX.X)	XX (XX.X)

**Appendix Table 2:** Kaplan-Meier analyses comparing OS between ENCO+BINI cohorts in Columbus trial and Flatiron RWD

	Columbus Trial	Flatiron RWD
	ENCO+BINI	ENCO+BINI
	N =	N =
Summary of deaths, censoring and median survival		
Death, n (%)	XX (XX.X)	XX (XX.X)
Censored, n (%)	XX (XX.X)	XX (XX.X)
Median OS (95% CI)	XX (XX, XX)	XX (XX, XX)
Kaplan-Meier based estimates of % of patients remaining alive at different time points		
6 Months	XX	XX
12 Months	XX	XX
18 Months	XX	XX
24 Months	XX	XX
30 Months	XX	XX
36 Months	XX	XX

**Appendix Table 3:** Unadjusted and adjusted hazard ratios comparing OS between ENCO+BINI cohorts in Columbus trial and Flatiron RWD

Results from adjusted models in Appendix Table 3 will be based on multiple imputation via multivariate imputation by chained equations. Expected adjustment factors are listed below; specific functional forms/categorization of adjustment factors will be based on the data.

	Unadjusted model	Adjusted model
	HR (95% CI)	HR (95% CI)
Exposure variable		
ENCO+BINI in Columbus trial (ref. ENCO+BINI in Flatiron RWD)	X.XX (X.XX, X.XX)	X.XX (X.XX, X.XX)
Adjustment factors		
Age	-	X.XX (X.XX, X.XX)
Male vs female	-	X.XX (X.XX, X.XX)
Race	-	X.XX (X.XX, X.XX)
BMI		
Disease stage	-	X.XX (X.XX, X.XX)
ECOG	-	X.XX (X.XX, X.XX)
LDH	-	X.XX (X.XX, X.XX)
Time from first diagnosis to metastatic disease...		X.XX (X.XX, X.XX)
Time from metastatic disease to treatment initiation		
Use of prior therapies		X.XX (X.XX, X.XX)

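### The imputation model in Section 8.7.3 names only other baseline characteristics as predictors; leaving survival out attenuates the ECOG, LDH and stage effects and can shift the cohort hazard ratio in either direction

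*Combined protocol and SAP*

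**What the plan says.** Section 8.7.3 is the only description of the imputation model. After introducing it as a brief account, it says that each incomplete characteristic is imputed by "regressions of observed data for that characteristic on observed and imputed values of other baseline characteristics". ECOG, LDH and disease stage are the variables to be imputed. The list is left open, but on stated grounds: "Additional variables will be considered for inclusion in the MICE procedure based on their relevance for adjustment and degree of missingness".

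Section 8.7.4 then fits the multivariable Cox model for OS "using the Columbus trial dataset and each of the RWD datasets with imputed baseline characteristic values in turn" and pools the log HRs by Rubin's rules. COLUMBUS enters as observed; only Flatiron is imputed.

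No other place adds survival as a predictor:

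- Section 6 refers to "a multiple imputation approach that has been validated for Flatiron Health EHR data in metastatic melanoma" without giving its predictors.
- The note to Appendix Table 3 gives only the method: "Results from adjusted models in Appendix Table 3 will be based on multiple imputation via multivariate imputation by chained equations".
- Annex 1, "LIST OF STAND-ALONE DOCUMENTS", has the entry None.
- Section 5 treats protocol and SAP as a single milestone, so no later, fuller SAP is signalled.

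**The concern.** When a covariate is imputed for use in an outcome model, the imputation model has to contain the outcome. If it does not, the imputed values are, given the other predictors, unrelated to that patient's survival. The Cox model then estimates a mixture of the true association (observed values) and a weakened one (imputed values).

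Two results are exposed. The ECOG, LDH and stage HRs planned for Appendix Table 3 are biased towards 1. The cohort HR can also move, by two routes. Weakened coefficients under-adjust for any case-mix difference between the cohorts. In addition, one coefficient per covariate serves both cohorts although the weakening occurs only in Flatiron, so the cohort term can absorb some of the misfit even when case mix is equal. The two routes can add or cancel, so the direction is not known in advance.

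The cohort HR informs whether the two sources may be pooled, which Section 6 allows "provided outcomes are sufficiently consistent between CTD and RWD settings".

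**Working it through.** **No figure to reproduce.** The plan gives no Flatiron sample size, missingness rate, covariate effect or event count. The size of the effect was therefore examined by simulation.

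**Inputs from the plan**
- COLUMBUS n = 192 (Section 8.4).
- COLUMBUS follow-up: enrolment 30 December 2013 to 10 April 2015, lock 15 September 2020 (Section 8.4), giving 65.2 to 80.5 months.
- Flatiron follow-up: index after 27 June 2018 and at least 3 months before cutoff (Section 8.2.1); end taken as 01 January 2022, the example date in Table 1. This gives 3 to 42.2 months.
- Cohort HR is COLUMBUS versus Flatiron (Appendix Table 3).

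**Assumed inputs**
- Flatiron n = 250; true cohort HR 1; three correlated binary covariates with HRs 2.3, 1.7 and 1.6; one further covariate, fully observed.
- Missing in Flatiron only, 40/40/30% unless stated.
- Prevalences: COLUMBUS .30/.30/.60. Flatiron the same (balanced), .45/.45/.70 (sicker), .60/.60/.85 (much sicker) or .20/.20/.45 (healthier).
- Baseline hazard 0.011 per month, giving about 145 COLUMBUS and 84-134 Flatiron deaths.
- Early death means within 6 months; missingness in those patients multiplied by 1.75 (more) or 0.4 (less).

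**Models**
- As written: logit P(X_j = 1) = a + c'X_(other baseline).
- Outcome included: the same plus d1·D + d2·H(T), where D is the death indicator and H(t) = Σ_(t_i ≤ t) d_i/n_i is the Nelson-Aalen estimate.
- Analysis: h(t) = h0(t)·exp(θ·cohort + β'X), pooled by Rubin's rules.
- Shift = θ(imputed) − θ(complete data, same replicate). 600 replicates, 8 imputations, 6 cycles; Monte Carlo SE of the shift 0.001-0.002.

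**Cohort log HR, survival omitted**

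| Setting | Shift | Ratio of HRs, exp(shift) |
|---|---|---|
| Balanced | +0.034 | 1.035 |
| Flatiron sicker | -0.002 | 0.998 |
| Sicker, 60/60/50% missing | -0.011 | 0.989 |
| Much sicker | -0.041 | 0.960 |
| Healthier | +0.057 | 1.059 |
| Sicker, more missing in early deaths | -0.028 | 0.972 |
| Sicker, less missing in early deaths | +0.016 | 1.016 |

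The standard error of the cohort log HR was 0.15-0.16, so the largest shift is 0.057/0.15 ≈ 0.4 SE. Coverage of the 95% CI stayed at 94-96%.

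**Covariate effects.** With survival omitted, log HRs fell to 0.72-0.95 of complete-data values; an HR of 2.3 became 1.8-2.1. With survival included they were 0.97-1.01 of complete-data values, and the cohort shift lay between -0.013 and +0.003. In the two sicker settings with random missingness, both methods gave similarly small cohort shifts.

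**Repeat and sensitivity.** A separate run of the balanced, sicker, much sicker and healthier settings gave shifts of +0.034, -0.001, -0.039 and +0.058, with covariate log HRs at 0.81-0.95. With survival included the covariates returned to 0.98-1.02 and the larger shifts fell to between -0.015 and +0.006. With no ECOG values missing, LDH and stage were still attenuated and the cohort shift was about half.

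**Different assumptions.** A further simulation used Flatiron n = 200, missingness 30/30/20% or 50/60/40%, HRs 1.8 (ECOG), 2.2 (LDH) and 1.5 (stage), and wider case-mix contrasts.
- Survival omitted: log HRs fell to 78-92% (ECOG), 76-95% (LDH) and 86-97% (stage) of the true values. The cohort HR ranged from 0.92 to 1.08, against 0.98-1.00 with complete data. Shifts ran from -0.085 to +0.091; exp gives 0.92 to 1.10.
- Survival included: covariates 98-103% of true, cohort HR 0.97-1.01.
- Large samples (3840 and 4000), which isolate bias from small-sample noise: shifts -0.069 to +0.080 without survival, -0.003 to +0.012 with it.

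**The case against.** **The text is a summary.** The sentence is introduced as brief, survival is not expressly excluded, and both the cited imputation guidance and the earlier Flatiron work may include it. This stands as a limit: the plan's wording does not prove what was programmed. It does not remove the point. The only predictors named are baseline characteristics, neither stated ground for adding variables leads to the outcome, and a citation does not specify this study's model. A programmer following the text would leave survival out.

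**The primary result is little affected.** Largely true. Taking an SE of 0.155, a shift of 0.034 raises the root-mean-square error to √(0.155² + 0.034²) = 0.159 (about 2%), and 0.057 raises it to 0.165 (about 7%). The surest harm is to adjustment-factor HRs that no objective addresses. The pooling criterion has no threshold, so no shift can be shown to cross it.

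**The correction is not complete in small samples.** Also true. At Flatiron n = 100 with the heavier missingness, cohort shifts were -0.045 to +0.055 with survival included, against -0.043 to +0.098 without. The covariate effects were nonetheless recovered.

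**The simulations are simpler than the plan.** LDH in U/L and five-level stage were made binary, and a single covariate stood in for all the fully observed ones in the main simulation. Section 8.2.1 also requires ECOG 0 or 1 at index, which read strictly leaves little ECOG to impute, although Table 1, Section 8.7.3 and the Appendix Table 1 shell all allow it to be missing. The sizes are therefore illustrative. The attenuation does not depend on these choices and persisted for LDH and stage with ECOG complete.

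**Conclusion.** The concern holds. Carried out as written, Section 8.7.3 leaves survival out of the imputation and biases the ECOG, LDH and stage HRs towards 1. The simulated retention of the log HR was 0.72-0.97 across all the assumptions tried at Flatiron n = 200 to 250. The cohort HR can move either way: -4% to +6% in the main settings and about -8% to +10% under wider case-mix contrasts. It can also be close to zero.

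These sizes rest on assumed Flatiron numbers, missingness, covariate effects and case mix, so confidence in them is medium. The defect should be corrected because it acts on the comparison that informs pooling and costs little to address. It is unlikely to change the conclusion by itself.

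**What to change.** State in Section 8.7.3 that every Flatiron imputation regression includes:

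- the death indicator;
- the Nelson-Aalen cumulative hazard at the patient's OS time;
- all covariates of the adjusted Cox model in Section 8.7.4.

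Imputation that is compatible with the Cox model is an acceptable alternative. If any COLUMBUS adjustment covariate proves to be missing, impute it in the same way.

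Section 8.7.5 says that, if PFS is judged suitable, "unadjusted and adjusted comparisons of PFS will be conducted using the methods described in Sections 8.7.2 and 8.7.4". For that analysis, use the PFS indicator and its cumulative hazard in the imputation, and say that the post-imputation Appendix Table 1 is built from the OS imputation set.

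For OS the cost is one or two sentences and two derived columns. The eligibility criteria already require mortality data for every included patient, so no new data are needed. A second imputation set is needed only if the PFS comparison goes ahead. If survival was always meant to be included, the change simply records it.

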#### **8.7.4. Adjusted analysis of OS between ENCO+BINI cohorts in Columbus trial versus in Flatiron RWD**

Finally, an adjusted comparison of OS between ENCO+BINI cohorts in the Columbus trial and Flatiron RWD will be conducted. Hazard ratios will be estimated based on a multivariable Cox proportional hazard model, adjusting for key baseline characteristics known or expected to be related to OS in metastatic melanoma (e.g., age, sex, race, body mass index, ECOG performance score, disease stage, LDH, time from diagnosis to metastatic disease, time from metastatic diagnosis to ENCO+BINI initiation and use of prior therapies). Specific adjustment factors listed here may be revised based on expert clinical input.

The adjusted analyses will be conducted using the Columbus trial dataset and each of the RWD datasets with imputed baseline characteristic values in turn. Log-hazard ratios for the difference in OS with ENCO+BINI between the Columbus trial and each imputed dataset will be obtained, and a summary HR obtained by pooling results across all imputed datasets will be generated using Rubin's rules.

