#### 8.2.1. Inclusion criteria

Inclusion criteria are provided separately for the 2 data sources below. Key inclusion criteria in the COLUMBUS trial were:

- Histologically confirmed diagnosis of locally advanced, unresectable, or metastatic cutaneous melanoma or unknown primary melanoma

- American Joint Committee on Cancer (AJCC) disease stage of IIIB, IIIC, IVM1a, IVM1b, or IVM1c at trial enrolment
- Presence of BRAF V600E or V600K mutation in tumor tissue prior to enrollment
- At least 18 years of age at randomization
- Eastern Cooperative Oncology Group (ECOG) status of 0 or 1 at randomization
- Treatment naive or had progressed on or after previous first-line (1L) immunotherapy at randomization

Patients from the COLUMBUS trial included in this analysis will be those patients:

- Randomized to ENCO+BINI arm of the trial to receive 450mg once daily encorafenib and 45mg twice daily binimatinib combination therapy, and
- With available data on mortality

Pfizer has contracted with Flatiron for a custom data extract containing information on patients with advanced melanoma. Key inclusion criteria from the COLUMBUS trial will be applied to the Flatiron RWD population to align the populations to the extent possible between the 2 data sources.

Eligibility criteria applied to the Flatiron custom data extracted received by Pfizer included:

- Diagnosis of melanoma (International Classification of Diseases 9th or 10th Revision Clinical Modification - ICD-9-CM: 172.X; ICD-10-CM: C43.x) and secondary malignancy or metastasis (ICD-9-CM: 196.x, 197.x, 198.x; ICD-10-CM: C77.x, C78.x, C79.x).
- Confirmed BRAF V600E/V600K activating mutation reported in the data based on laboratory or genetic analysis results.
- At least 1 order or administration of ENCO+BINI treatment after the diagnosis of metastatic melanoma and within the available data cut period (01 January 2011 to 01 January 2022)
- Order or administration of ENCO+BINI treatment at least 3 months prior to the data cutoff date (e.g., 01 October 2022)

The sample of patients from the Flatiron health EHR data for this study will be identified using the following additional criteria applied to the custom data cut received from Flatiron:

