#### 8.4. Data sources

##### COLUMBUS trial

COLUMBUS was a two-part, multicenter, randomized, open-label, Phase 3 clinical trial. Part 1 of the trial investigated the effectiveness and safety of three treatment regimens in patients with locally advanced unresectable or metastatic BRAFV600-mutant metastatic melanoma who were treatment naïve or whose cancer had progressed after 1L IO. In Part 1 of the trial, patients were randomized to one of three treatment arms: 1) 450mg once daily encorafenib and 45mg twice daily binimatinib (n=192), 2) 960mg twice daily vemurafenib (n=191) and 3) 300mg once daily encorafenib (n=194). Randomization was stratified by AJCC disease stage (IIIB, IIIC, IVM1a, IVM1b, or IVM1c), ECOG performance status (0, 1), and BRAFV600 mutation profile (V600E, V600K). Progression-free survival was the primary endpoint in the trial, while OS was one of the secondary endpoints. Patients were enrolled in Part 1 of the trial between 30 December 2013 through 10 April 2015.

The ENCO+BINI arm of Part 1 of the trial will be used in this study (database lock date: 15 September 2020). Part 2 of the trial compared encorafenib 300mg once daily plus binimatinib 45mg twice daily versus encorafenib 300mg once daily alone and will not be considered.

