## APPENDIX: TABLE SHELLS

**Appendix Table 1:** Baseline patient characteristics for ENCO+BINI cohorts in Columbus trial versus in Flatiron RWD

Appendix Table 1 as illustrated below will be generated both before and after imputation of missing data.

	Columbus trial ENCO+BINI	Flatiron RWD ENCO+BINI
	N =	N =
Demographic Characteristics		
Age (years)		
Mean (SD)	XX.X (XX.X)	XX.X (XX.X)
Median (IQR)	XX.X (XX.X, XX.X)	XX.X (XX.X, XX.X)
Sex, n (%)		
Female	XX (XX.X)	XX (XX.X)
Male	XX (XX.X)	XX (XX.X)
Missing, n (%)	XX (XX.X)	XX (XX.X)
Race, n (%)		
White/Caucasian	XX (XX.X)	XX (XX.X)
Black/African American	XX (XX.X)	XX (XX.X)
Asian	XX (XX.X)	XX (XX.X)
Native American or Pacific Islander	XX (XX.X)	XX (XX.X)
Other	XX (XX.X)	XX (XX.X)
Missing	XX (XX.X)	XX (XX.X)
Ethnicity, n (%)		
Hispanic/Latino	XX (XX.X)	XX (XX.X)
Not Hispanic/Latino	XX (XX.X)	XX (XX.X)
Missing	XX (XX.X)	XX (XX.X)
BMI (kg/m  )		
Mean (SD)	XX.X (XX.X)	XX.X (XX.X)
Median (IQR)	XX.X (XX.X, XX.X)	XX.X (XX.X, XX.X)
Missing, n (%)	XX (XX.X)	XX (XX.X)
Year of treatment initiation, n (%)		
2011	XX (XX.X)	XX (XX.X)
2012	XX (XX.X)	XX (XX.X)
2013	XX (XX.X)	XX (XX.X)
2014	XX (XX.X)	XX (XX.X)
2015	XX (XX.X)	XX (XX.X)
2016	XX (XX.X)	XX (XX.X)
2017	XX (XX.X)	XX (XX.X)
2018	XX (XX.X)	XX (XX.X)
2019	XX (XX.X)	XX (XX.X)
2020	XX (XX.X)	XX (XX.X)
2021	XX (XX.X)	XX (XX.X)
2022	XX (XX.X)	XX (XX.X)
Geographic location, n (%)		
North America	XX (XX.X)	XX (XX.X)

Europe	XX (XX.X)	XX (XX.X)
Australia	XX (XX.X)	XX (XX.X)
Other	XX (XX.X)	XX (XX.X)
Missing	XX (XX.X)	XX (XX.X)
Disease-Related Characteristics		
Mean (SD)	XX.X (XX.X)	XX.X (XX.X)
Median (IQR)	XX.X (XX.X, XX.X)	XX.X (XX.X, XX.X)
Missing, n (%)	XX (XX.X)	XX (XX.X)
Time from metastatic melanoma diagnosis to treatment initiation (months)		
Mean (SD)	XX.X (XX.X)	XX.X (XX.X)
Median (IQR)	XX.X (XX.X, XX.X)	XX.X (XX.X, XX.X)
Missing, n (%)	XX (XX.X)	XX (XX.X)
BRAF+ mutation		
V600E	XX (XX.X)	XX (XX.X)
V600K	XX (XX.X)	XX (XX.X)
ECOG performance status, n (%)		
0	XX (XX.X)	XX (XX.X)
1	XX (XX.X)	XX (XX.X)
≥2	XX (XX.X)	XX (XX.X)
Missing	XX (XX.X)	XX (XX.X)
AJCC stage, n (%)		
Stage IIIB	XX (XX.X)	XX (XX.X)
Stage IIIC	XX (XX.X)	XX (XX.X)
Stage IV	XX (XX.X)	XX (XX.X)
Missing	XX (XX.X)	XX (XX.X)
LDH (U/L)		
Mean (SD)	XX.X (XX.X)	XX.X (XX.X)
Median (IQR)	XX.X (XX.X, XX.X)	XX.X (XX.X, XX.X)
Missing, n (%)	XX (XX.X)	XX (XX.X)
LDH Level, n (%)		
Low	XX (XX.X)	XX (XX.X)
Normal	XX (XX.X)	XX (XX.X)
High	XX (XX.X)	XX (XX.X)
Missing	XX (XX.X)	XX (XX.X)

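### BRAF V600E versus V600K, a COLUMBUS stratification factor due to be tabulated in both cohorts, is not prespecified as an adjustment factor for OS

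*Combined protocol and SAP*

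**What the plan says.** Section 8.4 describes the trial's design: "Randomization was stratified by AJCC disease stage (IIIB, IIIC, IVM1a, IVM1b, or IVM1c), ECOG performance status (0, 1), and BRAFV600 mutation profile (V600E, V600K").

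Both sources require a qualifying mutation (Section 8.2.1). The COLUMBUS criterion is "Presence of BRAF V600E or V600K mutation in tumor tissue prior to enrollment". The criterion for the Flatiron extract is "Confirmed BRAF V600E/V600K activating mutation reported in the data based on laboratory or genetic analysis results".

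The block headed "BRAF+ mutation" in Appendix Table 1 has one row for V600E and one for V600K, each with a COLUMBUS and a Flatiron column. It has no row for missing values.

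The adjusted OS model in Section 8.7.4 offers, as examples, "age, sex, race, body mass index, ECOG performance score, disease stage, LDH, time from diagnosis to metastatic disease", then time from metastatic diagnosis to treatment and prior therapies. It adds: "Specific adjustment factors listed here may be revised based on expert clinical input". The shell for the adjusted results, Appendix Table 3, states "Expected adjustment factors are listed below" and leaves functional form and categorisation to the data. It has no row for mutation subtype, and Table 1 in Section 8.3 has no entry for it. No reason is given.

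**The concern.** This is a non-randomised comparison of one trial arm with a real-world cohort, so covariate adjustment is the main protection against differences in case mix. Requiring V600E or V600K in both sources restricts each cohort to those two subtypes. It does not make the mix of the two the same.

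If the mix differs and the subtypes differ in OS, part of any difference between settings would reflect mutation type. The adjusted hazard ratio is meant to put real-world effectiveness in context and to inform whether the two sources can be pooled, so an avoidable source of difference is worth removing. Section 8.9 does not cover this gap: its caveat on residual differences concerns factors that are unmeasured or unavailable in one of the sources, whereas Appendix Table 1 expects the subtype in both.

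**Working it through.** **Step 1. Compare the lists.**

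| Place | Stage | ECOG | V600E vs V600K |
|---|---|---|---|
| COLUMBUS stratification (8.4) | yes | yes | yes |
| Table 1 (8.3) | yes | yes | no |
| Appendix Table 1, both cohorts | yes | yes | yes |
| Variables named for imputation (8.7.3) | yes | yes | no |
| Adjustment list (8.7.4) | yes | yes | no |
| Appendix Table 3 | yes | yes | no |

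Two of the three stratification factors appear everywhere. The third appears only in the trial description and the descriptive shell.

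**Step 2. How firm are the adjustment lists?** Section 8.7.4 is introduced as a set of examples and can be revised on clinical input. Appendix Table 3 is firmer: it names the expected factors and leaves only their form to the data. An analyst who followed the expected list would not adjust for subtype. An analyst who added it after seeing Appendix Table 1 would be choosing a covariate on the basis of the data.

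**Step 3. Possible size.** The plan states no figure to reproduce: no V600K share, no OS effect of subtype, no sample size and no event count. Everything below rests on assumed inputs. For an omitted binary factor, the approximate multiplier on the hazard ratio for COLUMBUS with Flatiron as reference (the direction used in Appendix Table 3) is

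[1 + pC(h − 1)] / [1 + pF(h − 1)],

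where pC and pF are the V600K shares in COLUMBUS and Flatiron, and h is the OS hazard ratio for V600K versus V600E. With pC = 0.10:

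| pF | h = 1.2 | h = 1.5 |
|---|---|---|
| 0.05 | 1.02/1.01 = 1.010 | 1.05/1.025 = 1.024 |
| 0.10 | 1.000 | 1.000 |
| 0.15 | 1.02/1.03 = 0.990 | 1.05/1.075 = 0.977 |
| 0.20 | 1.02/1.04 = 0.981 | 1.05/1.10 = 0.955 |

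If Flatiron has the 10% share and COLUMBUS has 15-20%, the multiplier runs from 1.03/1.02 = 1.010 to 1.10/1.05 = 1.048. A difference of 5-10 points therefore shifts the hazard ratio by about 1-5%, in a direction set by which cohort has more V600K.

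More extreme assumptions give more: h = 2.0 with pF = 0.25 gives 1.10/1.25 = 0.880, a shift of 12%. Nothing in the documents makes that case likely. The formula also takes no account of whatever part of a subtype effect is already carried by stage, ECOG, LDH and the other listed covariates.

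**The case against.** The strongest case against is that the documents do not show the subtype to be a confounder. Section 8.7.4 selects factors for a known or expected relation to OS, and no section says that V600E and V600K differ in OS. A reader might infer from the stratification that the trial's designers judged subtype prognostic for survival. Section 8.4 gives no reason for the choice, and PFS was the primary endpoint, with OS secondary. Nor does stratification itself oblige anyone to adjust when only one arm is used. This stands: stratification is a reason to consider the factor, not evidence of its effect.

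A reader might also infer that the plan excludes the subtype. It does not, because the 8.7.4 list is illustrative and revisable. What remains is that the factor is not named in advance.

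A third inference is that Flatiron certainly holds the two subtypes separately. The eligibility wording could describe a combined flag, and the only sign of separate coding is an unfilled table shell. Section 8.7.1 also makes the summaries depend on availability in both sources. This stands too, and it is why the fix has two branches.

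The absence from Table 1 is weak evidence on its own. That table is presented as the key variables, and geographic location is likewise in Appendix Table 1 but not in Table 1.

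Finally, the shift is small beside likely precision. Assuming 130 trial deaths and 50-100 real-world deaths (not in the documents), the 95% limits lie at a factor of exp(1.96 × √(1/130 + 1/100)) = 1.30 to exp(1.96 × √(1/130 + 1/50)) = 1.39 either side of the estimate. The plan states no margin that a shift of 1-5% could cross. This limits the priority of the point. It does not supply a reason for leaving the factor unnamed.

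**Conclusion.** The point holds as an inexpensive improvement, with low to medium confidence that it would matter. BRAF V600E versus V600K is the only COLUMBUS stratification factor not prespecified for adjustment, although the plan intends to tabulate it in both cohorts, and no reason is given.

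Its effect on the hazard ratio is unknown. The figure of about 1-5% in either direction rests on an assumed 10% share in one cohort, a difference of 5-10 points and a subtype hazard ratio of 1.2-1.5. It is zero if the shares are equal or if subtype has no effect on OS. The documents do not support saying that the OS comparison is materially biased.

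**What to change.** Before the analysis, establish whether the Flatiron extract separates V600E from V600K.

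- **If it does:** add V600E versus V600K to Table 1, to the adjustment list in Section 8.7.4 and to Appendix Table 3. If the subtype is missing for some Flatiron patients, add it to the chained-equations imputation as well; Section 8.7.3 already allows further variables.
- **If it holds only a combined flag:** remove the separate Flatiron entries from the mutation rows of Appendix Table 1 and list the subtype in Section 8.9 among the factors that could not be adjusted for.

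The cost of the first branch is one extra model parameter, on top of about ten listed factors, and a few lines of text. Because study size is not stated, the effect of that parameter on precision cannot be calculated, but it should be small. The second branch costs only text.
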